5. INTRODUCTION

In 2015, an estimated 8.1 to 10.3 million Japanese had peripheral artery disease (PAD).⁴ The prevalence of this disease, often referred to as arteriosclerosis obliterans (ASO), is expected to increase up to 11.9 million by 2030.⁴ PAD of the lower extremities is caused by atherosclerosis and the prevalence of atherosclerotic risk factors, such as advanced age, diabetes, kidney disease, and smoking which are on the rise in Japan.^{4,5} Compared to non-PAD patients, within the first year of diagnosis PAD patients have a significantly higher risk of adverse cardiovascular events, including ischemic stroke and myocardial infarction, and significantly greater health care utilization and total annual healthcare costs.⁶ Thus, PAD poses a significant clinical and economic burden in Japan.

Revascularization is a crucial component for the treatment of patients with PAD, including those with claudication and the more advanced form of the disease, critical limb ischemia (CLI).⁷ Endovascular intervention may reduce limb pain, improve quality of life, and prolong walking distance for patients with claudication and has been associated with lower amputation rates in patients with CLI.⁸ However, the disease severity and anatomical location strongly influence the technical challenges and expected outcomes of the treatment.⁷ In particular, calcification represents a significant challenge to current endovascular device strategies and is associated with increased procedure-related adverse events, as well as poor long-term clinical outcomes^{2,9}. In the CODE Study, severe calcification in a $\geq 180^\circ$ arc prevented successful dilation of superficial femoral artery (SFA) lesions with either plain balloon angioplasty or a nitinol stent.¹⁰ Balloon angioplasty (BA) of calcified lesions is limited by acute vessel recoil, frequent flow-limiting dissections, high rate of perforation, and poor primary and secondary patency rates.^{2,11,12} For example, in a small study of 67 patients with 62% of them having severely calcified femoropopliteal lesions, the aggressive predilation of the calcified plaque led to a 59% perforation rate.¹² Furthermore, 40-50% of the BA cases require bailout-stenting; in the Resilient and Zilver trials, 48.3% and 57% of the lesions were moderately or severely calcified in the BA arm, respectively; of the patients in the BA arm, 40.3% and 50.4% required bail-out stenting.^{13,14} It is known that calcification increases the risk of stent fractures [*with consecutive thrombosis and vessel occlusion¹⁵*], which is associated with a higher in-stent restenosis (ISR) and reocclusion rate.¹⁶ In addition, the presence of rigid calcified plaques may result in incomplete and/or eccentric stent expansion and significant residual stenosis, which again increases the risk of in-stent restenosis and thrombosis.^{2,15,17} Drug-coated balloons (DCB) could be the solution to stent-related adverse events in calcified lesions [*leaving nothing behind*], as well as in reducing the high restenosis rates after BA [*the antiproliferative drug reduces neointimal hyperplasia, resulting in a lower incidence of restenosis and target lesion revascularization¹⁸*]. However, Fanelli et al. found that calcium represents a barrier to optimal drug absorption.¹⁹ Circumferential distribution seems to be the most influencing factor with the lowest primary patency rate and higher late lumen loss in 360° calcium presence. Based on the above, a new endovascular technique [*vessel preparation prior to DCB angioplasty*], such as CSI's OAS, is available for the treatment of severely calcified lesions. The findings of a recently published study suggest, that vessel preparation with orbital atherectomy prior DCB angioplasty may enhance the effect of DCBs in calcified lesions, reducing the need for stents and maintaining acceptable patency rates.²⁰

Calcific plaque is common in lower extremity arteries; in a recent analysis of 394 Japanese PAD patients who underwent endovascular therapy for SFA lesions, calcification was present in 46% of the lesions.⁹

In the US, CSI currently has approval for its Peripheral OAS (Class II). The prospective multicenter Clinical Study of the OAS for the Treatment of Peripheral Vascular Stenosis (OASIS) was conducted to evaluate the safety and effectiveness of the orbital atherectomy (OA) in patients with symptomatic PAD. One hundred twenty-four (124) patients from seventeen (17) contributing centers were enrolled, and two hundred and one (201) lesions were treated with OA. For additional information about the OASIS study and other CSI peripheral studies, please refer to the study Investigator's Brochure (IB).

6. DEVICE DESCRIPTION

6.1 Device Name and Indications for Use

The CSI Peripheral Orbital Atherectomy System (OAS) is a percutaneous orbital atherectomy system indicated for use as therapy in patients with calcified occlusive atherosclerotic disease in peripheral arteries and who are acceptable candidates for percutaneous transluminal atherectomy.

6.2 Device History and Description

The orbital atherectomy device (OAD) consists of a diamond-coated abrasive head (referred to as a "crown") mounted on the driveshaft that is designed to track and spin over the CSI Peripheral OAS Guide Wire, which can be independently advanced and steered. The OAD ablates occlusive material (i.e., peripheral plaque) and improves luminal patency. The diameter of the crown's orbit is a function of crown mass and rotational speed. During rotation, centrifugal forces press the crown laterally against the peripheral plaque, reducing a thin layer of that plaque on the vessel wall.

The first-generation model of the CSI Peripheral OAS received CE Mark in February 2007 and US FDA 510(k) clearance in August 2007 for use as therapy in patients with occlusive atherosclerotic disease in peripheral arteries and who are acceptable candidates for percutaneous transluminal atherectomy. The Peripheral OAS is commercially available in the US, Germany, Austria, France, Malaysia, Singapore, and United Arab Emirates.

The current generation model of the CSI Peripheral OAS intended to be used in KAIZEN received US FDA clearance in July 2019. The components of the OAS are described below.

- CSI Peripheral Orbital Atherectomy Device (OAD) is a hand-held component of the OAS that provides the physician with independent control of the OAS. The OAD is a single use over-the-wire device consisting of a handle, and a saline line (**Table 1**).
 - The OAD handle includes a sheath-covered drive shaft and a diamond-coated crown. The OAD crown can pass in tight lesions, smaller than the crown size, due to its angular front sanding edge and the OAD's mechanism of action. The handle

includes control buttons for operating the OAD and contains the motor and electronics that power the rotation of the drive shaft. The crown is a diamond-coated, abrasive surface mounted on the driveshaft that is designed to track and spin over the guide wire and remove or reduce the occlusive tissue into microscopic particles (**Table 2**).

- CSI OAS Pump (OAS Pump model number SIP-3000) provides the saline/lubricant pumping mechanism and power to the device. The small, reusable, and portable OAS Pump attaches to a standard five-wheel rolling intravenous (IV) pole and plugs into a wall power outlet. The OAS Pump includes a built-in audible 25 second spin time notification, system power and priming buttons, and status indicators.
 - ***Note: OAS Pump was approved for use with CSI's Coronary OAS in Japan in June 2018.***
- CSI OAS Peripheral Guide Wires are single-use, smooth, stainless steel wires, with a silicone coating, and a radiopaque distal spring tip (**Table 3**). The OAS Peripheral Guide Wire allows for proper positioning of the OAD crown within peripheral arteries and provides a center of rotation for the OAD drive shaft. The OAS Peripheral Guide Wires are provided sterile.
- CSI OAS Lubricant (model number VPR-SLD2) is designed to reduce the friction between the flexible drive shaft of the CSI OAD and CSI Peripheral Guide Wire. The CSI OAS Lubricant is an emulsion composed of soybean oil, egg yolk phospholipids, glycerin, and water for injection. An addition of sodium hydroxide adjusts the pH resulting in a final pH of 8.0 with a pH range of 6.0 to 8.9. CSI OAS Lubricant is single use and provided sterile.
 - ***Note: CSI OAS Lubricant was approved for use with CSI's Coronary OAS in Japan in March 2017.***

Table 1: CSI Peripheral OAD Information

Parameter	Value
Electrical cable length: OAD to OAS pump	3.4 m approximately (11 ft)
Electrical Connector type (OAD power)	Type CF applied Part –DC barrel (48 V DC)
Fluid connector type	Polycarbonate Luer fitting
Saline line tubing length (from pump to OAD port)	3.2 m approximately (10.5 ft) minimum
Visual alerts	Speed indicators
Sterilization	Ethylene oxide (EtO) cycle
Storage conditions	Room temperature in a clean environment.
Operating conditions	Typical operating room/catheterization laboratory environment (10-30° C)
Operating life	8 minutes of total therapy time
Water Ingress Protection	IPX1: Protection against water ingress
Approximate saline flow rate for 145 cm (4 Fr) OAD	6 mL/min to 16 mL/min
Approximate saline flow rate for 145 cm (5 Fr and 6 Fr) OAD	5 mL/min to 30 mL/min

Table 2: OAD Crown Information

Model Number	Crown Diameter (mm)	Crown Type	Shaft Length (cm)	Nose Length (mm)**	OAD Maximum Outer Diameter (mm)	Recommended Introducer Sheath Internal Diameter, Fr	Rotational Speeds (rpm) +/- 10%
DBP-125SOLID145	1.25	Solid	145	7	1.32	4	60,000 90,000 120,000
DBP-150SOLID145	1.50	Solid	145	10	1.60	5	60,000 90,000 120,000
DBP-200SOLID145	2.00	Solid	145	30	2.00	6	60,000 90,000 120,000

**Each crown size has a specific nose length. (Nose length is the length of the drive shaft from the crown to the shaft tip).

Table 3: CSI OAS Peripheral Guide Wire Information

Model	Guide Wire Length	Core wire diameter	Spring Tip Length	Spring Tip Diameter	OAD Device Shaft Length Compatibility
VPR-GW-14	335 cm	.014"	3 cm	.014"	145 cm
VPR-GW-17	335 cm	.014"	3 cm	.017"	145 cm

6.3 Principles of Operation

The OAS is designed to reduce occlusive material and improve lumen patency by using a rotating, diamond-coated crown. The combination of the off-set crown mass and rapid rotation of the crown creates centrifugal forces that press the diamond-coated crown against the stenotic lesion. With each pass of the crown, the diameter of the vessel lumen increases in relation to the reduction of stenotic material. As the lumen diameter increases the centrifugal force decreases until a maximum orbit diameter is achieved. Actual final orbit and lumen diameter will depend on a variety of factors including run time, rotation speed, the composition of the lesion, and individual subject anatomy. For additional information regarding the OAS, please reference the Instructions for Use (IFU) and study IB. Note the IFU is contained within the study IB.

6.4 Devices Used in the Study

The device under investigation in this study is the CSI Peripheral OAS. Approximately one device per subject will be used.

In addition, the following commercially available products will also be used in the study:

- Intravascular Ultrasound (IVUS) system using DICOM modality with a high-definition imaging catheter (e.g., Phillips Eagle Eye® Platinum IVUS Catheter)
- POBA: Per physician's standard of care, any approved POBA is allowed
- DCB: Medtronic IN.PACT™ Admiral™ (Applies to "Devices used in Clinical Trial" in this study.)

Please refer to the appropriate-device-related IFU.

6.5 Manufacturer

The Sponsor and manufacturer of the device under investigation is:

Sponsor Name	Cardiovascular Systems, Inc.
Address	

6.6 Device Handling and Traceability

The investigational devices will be tracked from the time it is shipped from CSI until it is either used in a procedure on a study subject or returned to the Sponsor. To assist in the traceability of the investigational devices, each device is labeled with a Model number and Lot or Serial number.

6.7 Device Storage

All Investigational Devices must be stored in a locked/secure location with access limited only to applicable study staff. Refer to the IB for more information on device handling and storage.

6.8 Device Accountability

A Device Accountability Log and shipping records will be maintained at each study site. Investigational Devices allocated for site use will be recorded in the Device Accountability Log upon delivery to the study site until use. Each site will be responsible for tracking the receipt and disposition of all study devices. If there is a device accountability discrepancy, the Sponsor and site will work to reconcile the discrepancy. Documentation of reconciliation will be maintained.

The Device Accountability Log will be updated as devices are received, opened, used or returned.

Commercially available accessory products will not be required to be tracked on the Device Accountability Log.

6.9 Device Return

All unused/expired devices must be returned to CSI. Sites should contact their study representative to obtain further instruction on device return procedures. At the end of the study enrollment period, all remaining investigational devices and study supplies must be returned to CSI.

7. OBJECTIVE

The objective of the study is to collect safety and effectiveness data to support potential commercialization of the peripheral OAS device in Japan.

8. STUDY ENDPOINTS

8.1 Primary Endpoint

The primary endpoint will demonstrate OAS safety and efficacy via Acute Device Success.

Acute device success is defined post-procedure as the percentage of subjects with:

- a) ≤50% residual stenosis post OAD + POBA [Angiographic Core Lab assessed] and,
- b) No OAS-related severe angiographic complications defined as severe dissections (D-F), perforation, or distal emboli requiring additional treatment during the procedure [CEC adjudicated]

8.2 Secondary Endpoints

The following secondary endpoints will be evaluated:

1. Reduction in lesion stenosis both post-OAD and post-OAD+POBA [Angiographic Core Lab assessed] (absolute mean percentage change defined as the difference between the pre-procedure percent stenosis and the percent stenosis measured post-OAD and post-OAD+POBA)
2. Acute technical success defined per the PARC definition of achievement of a final residual stenosis <30% for stented and <50% for non-stented subjects by angiography at the end of the procedure [Angiographic Core Lab assessed] without severe angiographic complications defined as severe dissections (D-F), perforation, or distal emboli requiring additional treatment during the procedure [CEC adjudicated]
3. DCB Device Success defined as the ability to achieve successful delivery and deployment of all DCB to the target lesion as described per the Instructions for Use (IFU) within 3 minutes of insertion without removal and use of an additional device.
4. Target vessel patency at 6 months defined as absence of clinically-driven Target Lesion Revascularization (TLR) and ≤2.4 peak systolic velocity ratio (PSVR) as assessed by Duplex Ultrasound [Duplex Ultrasound Core Lab assessed]. Clinically-driven TLR is defined as repeat procedure performed for ≥50% stenosis confirmed by angiography within all or part of the target lesion after documentation of recurrent clinical symptoms of PAD following clinical trial treatment [CEC adjudicated]
5. Rate of severe angiographic complications defined as severe dissections (D-F), perforation, or distal emboli requiring additional treatment during the procedure [CEC adjudicated]
6. Acute procedure success defined as both acute technical success and absence of death, stroke, MI, acute onset of limb ischemia, index bypass graft or treated segment thrombosis, and/or need for urgent/emergent vascular surgery within 72 hours of the clinical trial treatment [CEC adjudicated]
7. Major Adverse Event (MAE) rate at 30 days and 6 months [CEC adjudicated] defined as:

- a) All-cause death through 30 days **or**
- b) Major amputation of the target limb **or**
- c) Clinically-driven TLR

8. Adverse Event rates at 30 days and 6 months [CEC adjudicated]
9. Distribution of Rutherford Classification compared to baseline at 30 days and 6 months
10. Change in Ankle Brachial Index (ABI) after clinical trial treatment compared to baseline

9. STUDY DESIGN

9.1 Description of Study Design

This prospective, single-arm, multi-center study is designed to evaluate the performance of the peripheral Orbital Atherectomy System (OAS) in the treatment of the adult Japanese population with a *de novo* symptomatic calcified occlusive atherosclerotic lesion in the SFA and/or POP arteries (**Figure 1**).

The KAIZEN study will use objective criteria to identify patients to be enrolled. The initial enrollment criteria will be assessed by the treating physician. An independent physician review of objective computer-aided imaging will determine final eligibility into the primary analyses.

The rationale for the single-armed study design is based on the significant amount of testing completed before human studies and the multiple human clinical trials that have assessed over 4000 subjects in the US. The peripheral OAS has a well-established safety and performance profile. The hypothesis-based performance goals chosen for this study are based on observed rates from previous study subjects and lesions similar to those expected to be enrolled in the KAIZEN study. It is expected that the results from this study will be similar to observed rates from other Peripheral OAS studies.

9.1.1 Study Duration

Subject participation in the study may last about 6 months.

9.1.2 Enrollment Criteria

Sixty-two (62) subjects who meet the enrollment criteria after an Independent Physician Review using objective computer-aided imaging are required for a proper assessment of the Primary Endpoint. The study may enroll at approximately (12) sites in Japan.

Additionally, KAIZEN includes an Independent Physician Reviewer who will verify the treating physician's assessment of eligibility criteria. The Independent Physician Reviewer will assess the angiographic and IVUS core laboratory results using objective computer-aided imaging to identify patients who will be included in the primary analysis of KAIZEN.

9.1.4 Study Hypothesis

The safety and efficacy of the OAS device will be evaluated by the rate of Acute Device Success (Section 8.1) against a pre-defined success criteria of 50% (Section 9.1.3). Comparisons will be made based on the following hypothesis test:

$$H_0: \pi_s \leq 50\%$$

$$H_a: \pi_s > 50\%$$

Where:

π_s = the probability of Acute Device Success

For the Acute Device Success endpoint, if the lower bound of the 95% confidence interval is >50%, the null hypothesis will be rejected, and the endpoint will be considered met.

9.1.5 Justification of the Sample Size

A sample of 62 subjects meeting Independent Physician Review is required to reject the null hypothesis (Table 5). The sample size was determined based on the following:

[REDACTED]

- Approximately 90% power
- A one-sided α -level of 0.025

Table 5: Sample Size Parameters and Justification

Endpoint	Anticipated Performance	Performance Goal	Power	Alpha (one-sided)	Sample Size
Acute Device Success	0.70	0.5	0.90	0.025	62

Subjects who are enrolled and treated may not meet Independent Physician Review. In order to ensure a primary analysis population of at least 62 subjects, sites will need to enroll and treat patients in excess of the required 62.

[REDACTED]
[REDACTED]
[REDACTED]
[REDACTED] Roll-in subject data will be reported separately.

Table 6: Sample Size Parameters and Justification

Endpoint	N		
Acute Device Success	62		

In order to minimize bias, a maximum of 25% of subjects may be enrolled at a single site, not including roll-in subjects. There is no minimum number of subjects required to be enrolled at each site.

10. DATA COLLECTION

10.1 Study Data Collection

The electronic case report forms (eCRF) for this study will be maintained in an electronic data capture (EDC) system. Site personnel who are trained and delegated the task will enter data from the subject's source documents stored in the subject's medical record into the eCRF accessed remotely via a secure internet connection. The PI will review and sign off on the data once entered into the eCRF. If changes are made to the data following PIs electronic signature, the eCRF will need to be re-signed. Data will be stored in a secure, password-protected database that will have the data archived daily.

Data will be reviewed by the study Sponsor for completeness, correctness and consistency using programmed and manual data checks. Data queries will be used to document data that are incomplete, inconsistent or unclear. Data queries may also be used to clarify if a deviation to the protocol had occurred. Data queries may be generated by the database, monitor, or Sponsor during data review. Table 7 below lists the tests and procedures required per protocol including timeframes.

Table 7: Summary of Required Tests and Procedures

Procedure / Test / Data Collection	Baseline	Before Clinical Trial Treatment	Clinical Trial Treatment ¹⁰	Discharge	30-Day Follow-up Assessment ⁸	6-Month Follow-up Visit ¹⁰
Visit Window	≤30 Days from Clinical Trial Treatment	Procedural (Values collected in Cath Lab)	After Clinical Trial Treatment and Before Discharge	+14 Days	+30 Days	
Informed Consent ¹	X					
General Inclusion / Exclusion Criteria	X					
Clinical Trial Treatment Inclusion / Exclusion Criteria		X				
Rutherford Classification	X				X ^{9, 12}	X ¹²
ABI Assessment	X			X ¹²		
Medical History with Demographics	X					
Physical Exam (Height/Weight)	X					
Medication Review	X			X	X ¹²	X ¹²
Angiography	X ^{3, 11}	X ^{5, 11}	X ¹¹			
IVUS	X ³	X ^{5, 6}	X			
Duplex Ultrasound						X ¹²
Clinical Trial Treatment Details			X			
Study Exit						X
Clinical Laboratory Test						
Serum Creatinine	X					
Platelet	X					
Pregnancy Test	X ⁴					
Other						
Adverse Events ²			X ⁷	X ⁷	X ⁷	X ⁷
Complaints/Device Deficiencies			X			
Protocol Deviations	X	X	X	X	X	X
Notes:						
1 Informed Consent must be collected prior to study-required testing or procedures that are not standard of care.						
2 The reporting of adverse events will begin once the CSI Peripheral Guide Wire enters the body (enrollment).						
3 Diagnostic images to determine General Inclusion Criteria can be taken ≤30 Days from Clinical Trial Treatment.						
All imaging needs to be reverified on the day of Clinical Trial Treatment.						
4 Pregnancy Test must be conducted ≤24 hours of the Clinical Trial Treatment for female subjects of childbearing potential (urine or blood).						

5 Verify Procedure eligibility, estimate treatment results, and determine complications (See Section 11 and 12 for further details). Subject must meet all Clinical Trial Treatment Inclusion/Exclusion Criteria prior to inserting the CSI Peripheral Guide Wire (enrollment).

6 IVUS must be attempted once; however, if IVUS cannot cross before clinical trial treatment, further procedural IVUS measurements are not required.

7 Submit appropriate source documents for review of Adverse Events.

8 30-Day Follow-up assessment can be in-hospital follow-up or telephone assessment.

9 Required if 30-day Follow-Up Assessment occurs in-hospital.

10 Subjects in whom a CSI Peripheral Guide Wire complication occurred while entering the body, or the OAD was never inserted, will have a 6-Month Follow-up visit or telephone follow-up assessment for adverse events only.

11 Angiographic images are required at all time-points noted in Appendix A: Imaging and Procedure Flow Chart even if angiography images are not used to determine Calcium Assessment.

12 Only required for Enrolled and Treated subjects.

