11.4.2 Clinical Trial Treatment Exclusion Criteria

31. Subject has had any Inflow treatment (ipsilateral iliac and/or common femoral artery) that was unsuccessful or had complications prior to OAS guidewire insertion per the following definition:
 - a) $> 50\%$ residual stenosis and/or
 - b) Presence of angiographically assessed dissection (type D-F), perforation, distal embolization, thrombus and/or slow flow/no reflow

32. Target lesion is a chronic total occlusion (CTO) [confirmed by visual estimate via angiography]
33. Subject has presence of any other hemodynamically significant lesions or asymptomatic lesions in the target limb requiring a planned surgical intervention or endovascular procedure 30-days after clinical trial treatment
34. Presence of aneurysm in the target vessel
35. Acute ischemia and/or acute thrombosis of the SFA and/or POP (P1 and/or P2) artery
36. Angiographic evidence of perforation prior to insertion of the CSI Peripheral OAS Guide Wire
37. Angiographic evidence of severe (type D-F) dissection prior to insertion of the CSI Peripheral OAS Guide Wire
38. Planned use of atherectomy (other than CSI Peripheral OAS), laser, other debulking devices, CTO devices, cutting balloons, scoring balloons, specialty balloons or similar devices in the target limb

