11.5 Before Clinical Trial Treatment

- **NON-TARGET LIMB** Non-target limb treatment must occur either greater than 30 days prior to the clinical trial treatment or greater than 30 days after the clinical trial treatment in the study according to **Section 12.4**.
- **INFLOW LESIONS IN THE TARGET LIMB** Inflow lesions (ipsilateral iliac and/or common femoral artery) in the target limb may be treated on the same day as the clinical trial treatment provided.
 - The inflow lesion must be successfully treated defined as residual stenosis \leq 50% without complications prior to insertion of the OAS guidewire in the target lesion to be revascularized. - **Refer to Clinical Trial Treatment Exclusion Criteria 31.**
 - The inflow lesion may only be treated with POBA or stenting.
 - Atherectomy, laser, other debulking devices, CTO devices, cutting balloons, scoring balloons, specialty balloons or similar devices cannot be used for the inflow treatment. - **Refer to Clinical Trial Treatment Exclusion Criteria 38.**
- **NON-INFLOW, NON-TARGET LESIONS IN THE TARGET LIMB**
 - Treatment of lesion(s) not considered Inflow or Target Lesion cannot occur on the day of the clinical trial treatment.
 - Non-target lesion treatment on the target limb must occur greater than 30 days after the clinical trial treatment in the study. - **Refer to General Exclusion Criteria 8 and 10.**
- Access artery by operator's preferred methodology for target limb treatment.

- Cross the lesion using the operator's preferred wire (CSI Peripheral OAS Guide Wire cannot be used at this point).
- Assess Clinical Trial Treatment Inclusion/Exclusion criteria including Calcium Assessment using IVUS and/or angiography – **Refer to Appendix A** to determine when IVUS and angiography images are taken.
 - IVUS Catheter – refer to IVUS IFU to determine appropriate IVUS catheter size.
 - One pass of the IVUS Catheter will be attempted in order to perform Calcium Assessment. If IVUS cannot cross the lesion, do not attempt crossing with IVUS again.
 - Ensure angiographic images have been collected.
 - To complete the Calcium Assessment, **Refer to Appendix B** to determine how to use data from IVUS and/or angiography to determine Calcium Assessment.
- Based on feedback from physician experts, there are no differences in patient characteristics that impact outcomes if calcium is measured by IVUS or angiography.
- Refer to **Figure 1** for the defined treatment area.

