 - If the subject, target lesion, or vessel does not meet ALL Clinical Trial Treatment Inclusion Criteria and/or meets ANY Clinical Trial Treatment Exclusion Criteria, the subject will not be included in the study and is considered a screen fail. The subject will be treated per physician's standard of care and will not be followed in the study or included in the analysis cohorts.
 - Recommended use of ruler to assess lesion length
- Refer to **Table 7** for Before Clinical Trial Treatment data collection requirements.

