### **7.7.8 Adverse Event (AE) Rates**

Adverse event rates will be assessed on a subject level for the mITT and FAS. All site reported and CEC adjudicated reportable adverse events specified in the protocol will be included in the analysis. Adverse events

are collected starting at enrollment through subject exit from the study. Adjudicated AEs will be summarized by AE term and overall for number and percent of subjects experiencing each event, and number of events.

Adverse events summaries will be provided for the time-points of enrollment to 30 days, and 31 days to study exit in the following groups:

- Serious Adverse Event (SAE): Any AE that the CEC has determined meets the protocol definition of serious
- Adverse Device Effect (ADE): Any AE the CEC has determined meets the protocol definition of related to the use of the OAS
- Serious Adverse Device Effect (SADE): Any ADE that the CEC has the protocol definition of serious
- Unanticipated Serious Adverse Device Effect (USADE): Any SAE that the CEC has determined that by its nature, incidence, severity or outcome has not been identified in the current version of the risk analysis report

Any events for which the determination of seriousness and/or relatedness to the device cannot be determined by the CEC will count as serious and/or related for the purposes of this analysis.

In addition, a subject data listing of all reportable AEs will be presented from the time of enrollment to study completion and will include the following: adverse event term, AE onset date, days to event, seriousness, relationship to OAS and procedure, outcome, and date resolved (if applicable).

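### Serious injury between the required IVUS attempt and guide-wire entry is not captured as an adverse event, and the subject leaves the study without follow-up

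*Protocol*

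**What the plan says.** Protocol Sections 11.3 and 11.4 put consent before the procedural eligibility check. In Section 11.5 the lesion is crossed with the operator's preferred wire, and the sponsor's wire is barred at this stage: "CSI Peripheral OAS Guide Wire cannot be used at this point". Then: "One pass of the IVUS Catheter will be attempted in order to perform Calcium Assessment". Table 7, note 6, makes the attempt compulsory: "IVUS must be attempted once".

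Adverse event reporting starts later, at entry of the sponsor's wire (Table 7, note 2): "The reporting of adverse events will begin once the CSI Peripheral Guide Wire enters the body (enrollment"). SAP 7.7.8 agrees that adverse events "are collected starting at enrollment through subject exit from the study".

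Section 11.4.2 excludes a subject with "Angiographic evidence of perforation prior to insertion of the CSI Peripheral OAS Guide Wire" (criterion 36). Criterion 37 does the same for a type D–F dissection. Under Section 11.5 a subject who meets an exclusion is a screen failure, is treated under standard of care and "will not be followed in the study or included in the analysis cohorts".

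**The concern.** The protocol adds an invasive step to the pathway and starts its safety record after that step. The two serious vessel injuries most relevant to passing a catheter through a tight, calcified lesion are also the two that remove the subject from the study at that point. The loss is therefore not random: these criteria select out subjects because they were injured.

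Section 24 asks the DMC to review safety data and advise on whether the study should go on. Section 7 gives the aim as safety and effectiveness data to support commercialization in Japan. If harm around a required step is not captured in usable form, the DMC has no routine sight of it. The final report would describe safety only from wire entry onward.

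**Working it through.** No figure in the documents is at issue, so the check is whether any provision closes the gap.

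1. **Timing.** Section 4 ends the pre-treatment period, and begins Clinical Trial Treatment, when the OAS guide wire enters the body. The eligibility IVUS attempt lies before that boundary and note 2 starts reporting at it. In Table 7 the Adverse Events row has no mark under Baseline or Before Clinical Trial Treatment. The Protocol Deviations row is marked in every column.
2. **Is the IVUS attempt a study requirement?** Yes. Note 6 makes it compulsory, Section 6.4 lists IVUS among products used in the study, and criterion 30 allows eligibility on angiography alone only after IVUS has failed to cross.
3. **Does Section 16.1 start earlier?** Its first item covers Clinical Trial Treatment events, which by definition begin at wire entry. Its all-SAE item gives no start date. The definition of an adverse event in Sections 4 and 16.2 is confined to subjects treated with an investigational or post-marketing study device.
4. **Does Section 16.4 start earlier?** It asks for reporting throughout participation, but sets no start before wire entry, and Section 11.5 ends involvement for screen failures.
5. **Does Section 16.5 help?** Its immediate-notification rule covers deficiencies of the study device and the drug-coated balloon, not the IVUS catheter.
6. **Is there any trace at all?** Possibly. Eligibility criteria, angiography and IVUS are marked in the pre-treatment column, and note 5 asks sites to determine complications on those images. An eligibility form could therefore show that criterion 36 or 37 was met. It would not supply cause, seriousness or outcome.
7. **How are neighbouring cases handled?** Under Section 12.1 and note 10, a subject with a complication from the sponsor's wire who never receives the atherectomy device is followed to 6 months for adverse events. The protocol thus already accepts safety follow-up without treatment; it begins one required step later.

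**Scale, on assumed inputs only.** Let n be the number of IVUS attempts and q the chance, per attempt, of a perforation or type D–F dissection in the window. Take n = 62, the required primary analysis population. This is a low figure, because more subjects must be enrolled than analysed and injured subjects screen-fail before enrollment. Assume q between 0.5% and 3%, independent across subjects.

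- Expected events, n × q: 62 × 0.005 = 0.31 to 62 × 0.03 = 1.86.
- Chance of at least one, 1 − (1 − q)^62: 27% at q = 0.5%, 46% at 1%, 71% at 2%, 85% at 3%.

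The documents support neither end of the range for q. The calculation shows only that zero events cannot be presumed.

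**The case against.** The strongest defence is that the start point is deliberate and coherent. The sponsor's wire is the first component of the investigational system to enter the body, IVUS is a commercially available product, and the adverse event definition is tied by citation to the Japanese device ordinance. Keeping earlier injury out of the device's record avoids charging it with harm it did not cause. Care is not withdrawn either: screen failures receive standard of care, Section 20.2.3 requires adequate medical care for adverse events, and Section 20.1 requires insurance for study-related injury. All of this stands. It is a good reason to keep these events out of the device's rates, but not a reason to leave them uncollected.

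A reader might go further than the documents allow in four ways:

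- *That the harm leaves no record at all.* The eligibility form may show it. What is missing is a safety record.
- *That everyone injured before wire entry is dropped.* Only those who meet an exclusion are. A type A–C dissection does not by itself exclude a subject, who can be enrolled and followed, although the injury still predates reporting.
- *That the DMC cannot see any IVUS harm.* Table 7 also marks IVUS during Clinical Trial Treatment, when events are collected.
- *That IVUS is the cause.* Criteria 36 and 37 name no cause. Wire crossing and optional same-day inflow treatment share the window, and the documents do not say whether IVUS is routine at the sites.

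The case report forms, the CEC and DMC charters and the Appendix A flow chart were not available. One of them could contain a partial remedy.

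**Conclusion.** The point holds as a gap in safety capture. Under the protocol and SAP as written, a perforation or type D–F dissection between the required IVUS attempt and wire entry is not collected as an adverse event. The subject is not followed, and no provision takes the event to the CEC or DMC. Lesser injuries in the same window also fall before the start of reporting.

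The number of such events is unknown, because the documents give no complication rate and do not state how many consented subjects will reach this step. How much of any harm would be due to IVUS is also unknown. No endpoint is miscalculated, and the sample size is untouched. This is a cheap improvement to the safety record; it does not challenge the primary result.

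**What to change.** - **Table 7, note 2:** for consented subjects, start collection of procedure-related adverse events and SAEs at insertion of the protocol-required IVUS catheter.
- **Section 11.5:** for those who then screen-fail, record each event through discharge, with presumed cause (IVUS, wire crossing or inflow treatment), seriousness and outcome. They stay outside all analysis sets.
- **Sections 16.1, 4 and 16.2:** align the list of events to collect and the adverse event definition. Because the definition is taken from the ordinance, a note creating a separate category of pre-enrollment procedural event may be simpler than rewording it.
- **SAP 7.7.8:** add a pre-enrollment listing of all these events, in enrolled and non-enrolled subjects, and send it to the DMC. The current summary periods begin at enrollment, so state that these events stay out of the device's adverse event rates and out of the mITT and FAS summaries.

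An injury already evident before the IVUS catheter goes in would remain outside this start point. The sponsor should say whether that is intended.

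Enrollment, analysis sets and the primary endpoint do not change. The cost is protocol and SAP wording, an event form for subjects with a pre-wire event, a little extra data entry and possibly a less favourable safety listing.
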